4.2 INCLUSION CRITERIA

Individuals who meet all of the following criteria are eligible for enrollment as study participants:

1. Participant must be able to understand and provide informed consent.
2. Adults age 18 to 65 years.
3. A clinical history of grass pollen-induced allergic rhinoconjunctivitis for at least 2 years with peak symptoms in May, June, or July.
4. A clinical history of moderate to severe rhinoconjunctivitis symptoms for at least 2 years interfering with usual daily activities or with sleep as defined according to the ARIA classification of rhinitis.
5. A clinical history of inadequately controlled rhinoconjunctivitis symptoms despite treatment with antihistamines and/or nasal corticosteroids during the grass pollen season for at least 2 years.
6. Positive skin prick test response at screening, defined as wheal diameter greater than or equal to 3 mm, to *Phleum pratense*.
7. Positive specific IgE at screening, defined as greater than or equal to IgE class 2 (0.7 kU/L) against *Phleum pratense*.
8. Removed in protocol version 3.0.

9. A woman of childbearing potential (WOCBP; for definition, see Appendix 6), regardless of birth control history, is required to consistently use one of the following highly effective methods of contraception throughout the study: hormonal (e.g. oral, transdermal, intravaginal, implant, or injection); intrauterine device (IUD) or system (IUS); vasectomized partner; bilateral tubal occlusion; or sexual abstinence (for definitions see contraceptive guidance in Appendix 6).

4.3 EXCLUSION CRITERIA

Individuals who meet any of these criteria are not eligible for enrollment as study participants:

1. Inability or unwillingness of a participant to give written informed consent or comply with study protocol.
2. Prebronchodilator forced expiratory volume (FEV₁) less than 70% of predicted value at either screening or baseline visit.
3. A clinical history of asthma requiring regular inhaled corticosteroids for > 4 weeks per year outside of the grass pollen season.
4. A clinical history of moderate to severe allergic rhinitis, as defined according to the ARIA classification of rhinitis, caused by either:
 - a. an allergen to which the participant is regularly exposed OR
 - b. tree pollen during tree pollen season treated with regular antihistamine or intranasal corticosteroids.
5. History of emergency visit or hospital admission for asthma in the previous 12 months.
6. History of chronic obstructive pulmonary disease.
7. History of recurrent acute sinusitis, defined as 2 episodes per year for the last 2 years, all of which required antibiotic treatment.
8. History of chronic sinusitis, defined as sinus symptoms lasting greater than 12 weeks that includes 2 or more major factors or 1 major factor and 2 minor factors. Major factors are defined as facial pain or pressure, nasal obstruction or blockage, nasal discharge or purulence or discolored postnasal discharge, purulence in nasal cavity, or impaired or loss of smell. Minor factors are defined as headache, fever, halitosis, fatigue, dental pain, cough, and ear pain, pressure, or fullness.
9. History of systemic disease affecting the immune system such as autoimmune diseases, immune complex disease or immunodeficiency.
10. Current symptoms of, or treatment for, upper respiratory tract infection, acute sinusitis, acute otitis media, or other relevant infectious process; serous otitis media is not an exclusion criterion. Participants may be re-evaluated for eligibility after symptoms resolve.
11. A past history of any malignant disease in the previous 5 years.

12. Any tobacco smoking within the last 6 months, or a history of greater than or equal to 10 pack years of cigarette use. Any vaping or electronic cigarette use within the last 6 months.
13. Previous immunotherapy with grass pollen allergen within the previous 5 years.
14. Previous treatment by dupilumab.
15. Previous Grade 4 anaphylaxis (WAO grading criteria) due to any cause.
16. History of anti-IgE, anti-IL-5, anti-IL-5 receptor, anti-IL-4/IL-13 receptor, or other monoclonal antibody treatment.
17. Current use of tricyclic antidepressants or monoamine oxidase inhibitors.
18. Ongoing systemic immunosuppressive treatment.
19. History of intolerance to the study therapy, rescue medications, or their excipients.
20. A positive pregnancy test.
21. Currently lactating/breast feeding.
22. The use of any investigational drug within 30 days of the screening visit.
23. The presence of any medical condition that the investigator deems incompatible with participation in the trial.
24. Past or current medical problems or findings from physical examination or laboratory testing that are not listed above, which, in the opinion of the investigator, may pose additional risks from participation in the study, may interfere with the participant's ability to comply with study requirements or may impact the quality or interpretation of the data obtained from the study.
25. Eosinophilic esophagitis or a diagnosis of any hypereosinophilic syndrome.
26. Administration of live attenuated vaccines within four weeks of dupilumab or dupilumab placebo injections, before the first injection and throughout the treatment period.

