Title	Grass Pollen Sublingual Tablet Immunotherapy plus Dupilumab for Induction of Tolerance in Adults with Moderate to Severe Seasonal Allergic Rhinitis
Short Title	Grass Pollen Immunotherapy plus Dupilumab for Tolerance Induction.
Clinical Phase	Phase II
Number of Sites	1 site
CTA Sponsor/Eudra Number	DAIT NIAID, 2018-003456-20
Study Objectives	The primary objective is to compare the effect of the combination of SLIT and dupilumab versus double-placebo on the nasal allergen challenge (NAC) response to grass pollen at year 3, one year after completion of study treatment.
Study Design	
This is a randomized, double blinded trial in adults (n=108) with moderate to severe seasonal allergic rhinitis with allergic sensitization to grass pollen.
 
Participants will be recruited from October 2020 through May 2021. Eligible participants will be randomized to one of the following 3 groups in a 1:1:1 ratio.
 
 • Combination of SLIT and dupilumab (n=36) • SLIT plus dupilumab placebo (n=36) • SLIT placebo plus dupilumab placebo (n=36) 
Grazax[®] is a sublingual grass immunotherapy product approved for clinical use in the United Kingdom and will be used as SLIT in this study. It (and its matching placebo) will be self-administered daily by participants through week 104. Dupixent[®] is the brand name for dupilumab and is a monoclonal antibody against the IL-4 receptor. Dupilumab and its placebo will be administered every two weeks by subcutaneous injection through week 104. With appropriate training by study personnel, alternate doses of dupilumab (and other occasional doses as required) may be self-administered by participants at home. Dupilumab is approved for self-administration by patients. The treatment phase of 104 weeks will be followed by an observation phase of 52 weeks.

Primary Endpoint	NAC (TNSS Area-under-Curve [AUC_{0-1hr}]) at year 3, one year after completion of treatment. The primary comparison will be between the combination of SLIT and dupilumab arm and the double-placebo arms (clinical tolerance endpoint).

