3. STUDY DESIGN

3.1 DESCRIPTION OF THE STUDY DESIGN

This is a randomized, double blinded trial in adults (n=108) with moderate to severe seasonal allergic rhinitis with allergic sensitization to grass pollen.

During the screening visit, participants will be asked for demographic information, complete a brief questionnaire concerning their allergic rhinitis, severity and duration, and impact on their quality of life, work or school performance and sleep. Any co-morbidities including asthma, eczema, or sinusitis; their past medical history; smoking history and medication history will be recorded. Participants will undergo skin prick testing with a panel of inhaled aeroallergens and with positive and negative controls. A blood sample will be taken for full blood count, total and specific IgE to grass and tree pollen, comprehensive chemistry and liver function tests.

[figure not shown]
Participants who meet eligibility criteria and choose to enroll will undergo a baseline visit. Thereafter participants will be randomized 1:1:1 to three parallel treatment arms as follows:

- Combination of SLIT and dupilumab (n=36)
- SLIT plus dupilumab placebo (n=36)
- SLIT placebo plus dupilumab placebo (i.e. double-placebo) (n=36)

Grazax[®] is a sublingual grass immunotherapy product approved for clinical use in the United Kingdom and will be used as SLIT in this study. It (and its matching placebo) will be self-administered daily by participants through week 104. Dupixent[®] is the brand name for dupilumab and is a monoclonal antibody against the IL-4 receptor. Dupilumab and its placebo will be administered every two weeks by subcutaneous injection through week 104. With appropriate training by study personnel, alternate doses of dupilumab (and other occasional doses as required) may be self-administered by participants at home. Dupilumab is approved for self-administration by patients. The treatment phase of 104 weeks will be followed by an observation phase of 52 weeks.

[figure not shown]
A NAC will be performed at baseline (Visit -1) and repeated annually after 1 and 2 years of study treatment and at 3 years (1 year after completion of study treatment). Annual NACs should be done at the same time every year, within +/-14 days of the preceding year's NAC. Blood, nasal brushings, and nasal fluid samples will be collected as outlined in Appendices 1 through 5.

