8.5 VISIT WINDOWS

All scheduled study visits will aim to occur within the time limits specified below and may be adjusted based on pollen count and participant availability.

Table 7. Visit Windows all Participants (See Appendices 1-5)

Visit	Visit description	Visit Window
Visit -4	Screening	October 2020 to January 2022
Visit -3	Rescue medication dispensing visit	April 1 to July 31
Visit -2	Baseline In-season assessments	June 1 to July 31
Visit -1	Baseline NAC	September to January
Visit 0	Randomization – 1 st dupilumab/dupilumab placebo dose	≥ 28 days after Visit -1 and before end of February
Visit 1	1 st SLIT/SLIT placebo dose	≥12 hours from Visit 0 and ≥ 7 days prior to Visit 2.
Visits 2-53	Treatment visits	Every 2 weeks from Visit 0 through week 104 +/- 10 days (with at least 7 days between treatment visits)
Visits 54-65	Observation visits	Every 4 weeks from 108 to 156 +/- 14 days
S1	Out of season visit assessment year 1	January to April
S2, S7, S12	Pre-season visit	April to May
S3, S8, S13	In-season visits	May to August
S4, S9, S14	Out-of-season NAC visits	September to January 1, 2 and 3 calendar years after Visit -1 +/- 14 days
S5, S10, S15	Mechanistic draws post NAC visits	≥ 4 weeks post NAC visit (S4, S9, S14) and before end of February each year
S6, S11	Out of Season visit	January to April

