12.4 COLLECTION AND RECORDING OF ADVERSE EVENTS

12.4.1 COLLECTION PERIOD

AEs/SAEs within 24 hours of study procedures will be collected during the screening period (visits -4 to visit -1). After the screening period, all AEs/SAEs will be collected from participants who undergo a baseline NAC (visit -1) until he/she completes study participation or until 30 days after he/she prematurely withdraws (without withdrawing consent) or is withdrawn from the study.

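### Exclusion 22 counts its 30 days from the screening visit, up to about 17 months before first dose, and no interval history or eligibility re-check is scheduled before the baseline challenge or randomisation

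*Protocol*

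**What the plan says.** Exclusion 22 (Protocol Section 4.3, repeated in the synopsis and in SAP Section 3) reads: "The use of any investigational drug within 30 days of the screening visit". Exclusion 5 reads: "History of emergency visit or hospital admission for asthma in the previous 12 months". Exclusion 12 covers smoking or vaping in the last 6 months. Exclusions 5 and 12 do not say from which visit they count back.

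On timing, the synopsis says: "Participants will be recruited from October 2020 through May 2021". The visit-window table in Section 8.5 gives the screening visit as "October 2020 to January 2022", the baseline in-season visit as "June 1 to July 31", the baseline challenge as September to January, and Visit 0 as "≥ 28 days after Visit -1 and before end of February".

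On eligibility, Section 3.1 puts it before the baseline visit: "Participants who meet eligibility criteria and choose to enroll will undergo a baseline visit". Section 8.3.1 places the assessment in the screening period, which Section 12.4.1 describes as Visits -4 to -1. Section 3.5 randomises only those who meet the criteria.

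On data capture, Appendix 1 marks medical and allergy history at Visit -4 only. Appendix 2 has no history or eligibility row at Visit 0. Under Section 12.4.1, adverse events between Visits -4 and -1 are collected only if they fall within 24 hours of a study procedure; after the baseline challenge all are collected. Concomitant medications are recorded at every visit (Section 8.3.1).

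**The concern.** A look-back for investigational drugs is there to keep residual effects of another product away from the first exposure in the trial. Here the first relevant exposures are the allergen challenge at Visit -1, the first injection at Visit 0 and the first tablet at Visit 1. A window fixed to Visit -4 describes the participant at a time that may be many months earlier.

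The protocol anchors some other criteria later: exclusion 2 (lung function) names screening or baseline, and exclusion 26 (live vaccines) is tied to the injections. Exclusion 22 is not.

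The history-based criteria raise a related but different question. The interval includes the 2021 grass pollen season, when asthma may worsen in these participants, yet nothing in the schedule prompts staff to ask again about emergency visits or smoking. Section 5.4.2 acknowledges a remote risk of asthma symptoms after the challenge, and Section 4.1 treats moderate-severe and uncontrolled perennial asthma as a contraindication to immunotherapy, so current asthma status matters at these visits.

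**Working it through.** The documents state no screening-to-randomisation interval, so there is no figure to reproduce. The check is calendar arithmetic on the visit windows, at 30.4375 days per month.

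**Year of the baseline windows.** Section 8.5 gives months without a year for Visits -1 and 0. SAP Section 9.2.6 names 2021 as the baseline season and 2022 as year 1, and Appendix 5 starts its schedule in January 2022. So Visit -1 falls between 1 September 2021 and 31 January 2022, and Visit 0 falls by 28 February 2022 (taking the last day of February as the limit).

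**Earliest Visit 0.** 1 September 2021 + 28 days = 29 September 2021.

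**Screening to Visit 0:**

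| Case | From | To | Days | Months |
|---|---|---|---|---|
| Longest | 1 Oct 2020 | 28 Feb 2022 | 515 | 16.9 |
| Shortest, synopsis recruitment window | 31 May 2021 | 29 Sep 2021 | 121 | 4.0 |
| Shortest, Section 8.5, with a baseline in-season visit | 31 Jul 2021 | 29 Sep 2021 | 60 | 2.0 |
| Shortest, Section 8.5, no in-season visit, Visits -4 and -1 on the same day (assumption) | 31 Jan 2022 | 28 Feb 2022 | 28 | 0.9 |

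**Does the 30-day window reach the challenge?** Take the reading most generous to the plan, 30 days on either side of screening.
- Screened on 31 May 2021: the window closes on 30 June, 63 days before the earliest challenge (1 September).
- Screened on 31 July 2021: it closes on 30 August, 2 days before the earliest challenge.
- Screened later than that: it can overlap the challenge, and in the 28-day case it also reaches Visit 0.

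So for anyone screened by 31 July 2021, and hence for everyone in the synopsis recruitment window, exclusion 22 covers neither the challenge nor the first dose.

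**Does another rule fill the gap?** Section 7.2 prohibits live vaccines, tricyclics, monoamine oxidase inhibitors, and monoclonal antibodies and other biologics. Exclusion 18 covers ongoing systemic immunosuppression. Appendix 7 sets washouts for named classes before the challenge. None bars investigational drugs as such. A non-biologic investigational drug outside those classes is left to investigator discretion under exclusions 23 and 24.

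**History.** A participant screened before 28 February 2021 and randomised on 28 February 2022 has the whole 12 months relevant to exclusion 5 falling after the only scheduled history.

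**The case against.** The strongest reply is that eligibility does not end at Visit -4. It is assessed across Visits -4 to -1, and only those who meet the criteria are randomised. Pregnancy tests are repeated at Visits -1 and 0, laboratory tests at Visit -1, and the physical examination at Visit 0. Spirometry may be done as late as Visit -1, although a footnote to Appendix 1 allows peak flow instead. Concomitant medications and their indications are recorded at every visit, so an investigational drug or treatment for an asthma attack has a place to appear. All adverse events are collected after the baseline challenge.

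Most of this stands, and it limits the point in three ways.

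- A reader might infer that someone who came to meet exclusion 5 or 12 after screening can be randomised under the rules. The documents do not support that: neither criterion is tied to screening, and a participant known to meet one is ineligible. The weakness is that the fact may never be asked for.
- A reader might infer that a distorted baseline challenge alters the mITT sample. It does not: mITT requires only a completed baseline challenge, and the symptom-score threshold for entry was removed in protocol version 3.0.
- A reader might infer bias in the primary comparison. Baseline TNSS AUC is measured before randomisation, so a residual drug effect on it is unrelated to assigned arm. It adds noise to a covariate and does not bias the contrast.

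The reply does not rescue exclusion 22. Recording an investigational drug under concomitant medications does not make the participant ineligible when the criterion looks only at the days around screening.

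**Conclusion.** The point holds in two parts of unequal strength. First, exclusion 22 is anchored to a visit that precedes first dose by up to 515 days. The minimum is 121 days on the synopsis window, or about 1 to 2 months under Section 8.5; the shortest case assumes no baseline in-season visit and same-day screening and challenge. A non-biologic investigational drug shortly before the challenge or first dose is allowed as written. Second, exclusions 5 and 12 have no stated reference date and no scheduled update of history, so interval events may be missed.

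The documents do not say how many participants could be affected, and the extreme intervals need extreme date pairings. Section 8.5 also lets visits move with pollen counts and availability. The consequence is a modest safety weakness at the challenge and first dose and possible noise in the baseline covariate. No sample-size figure depends on it. It is worth correcting because the correction is cheap, not because the primary analysis is at risk.

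**What to change.** - Reword exclusion 22 so that its 30 days count back from Visit -1 and from Visit 0.
- State that the look-backs in exclusions 5 and 12 run to Visit 0.
- Add a row for interval history and confirmation of eligibility at Visit -1 (before the challenge, Appendix 1) and Visit 0 (before randomisation, Appendix 2). It should ask about asthma emergency visits or admissions, smoking or vaping, and other trial participation.
- Reconcile the recruitment period in the synopsis (and SAP Section 3) with the screening window in Section 8.5.

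The cost is protocol wording and a few questions at two visits that participants already attend. The downside is that a few screened participants will be found ineligible late, before randomisation, and will have to be replaced from screening.

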4.4 SELECTION OF CLINICAL SITES/LABS

Imperial College London is in central London and readily accessible by public transport for the 3 million hay fever sufferers (1 in 4 of the London population of 12 million). The study is a natural extension of the successful GRASS trial which was a single center study located at Imperial College that targeted an identical study population and in which 108 participants were recruited from March to August (5 months) from the local clinic population and by advertisement in the local and national press and by the use of advertising on London Transport.

The group at Imperial College has a longstanding collaboration with the ITN and is experienced and fully equipped to fulfil the clinical and translational mechanistic aspects of the trial.

The primary outcome is an objective clinical surrogate, namely nasal allergen provocation that is standardized according to international guidelines and independent of

any local seasonal or geographic variations that might affect regional pollen counts and the generalizability of the findings. The potential limitations of using a single site have to be balanced against the heterogeneity in seasonal/environmental exposures, participant demographics, and study conduct/procedures that can complicate the conduct and interpretation of multi-center studies.

5. KNOWN AND POTENTIAL RISKS AND BENEFITS TO PARTICIPANTS

5.1 RISKS OF INVESTIGATIONAL PRODUCT OR INTERVENTION AS CITED IN INVESTIGATOR BROCHURE OR PACKAGE INSERT

5.1.1 SLIT: GRAZAX® AND GRAZAX® PLACEBO

Grazax® is approved for use in the UK for treatment of allergic rhinitis. Very commonly reported adverse reactions in adult and pediatric patients treated with Grazax® were local allergic reactions in the mouth which mostly were mild to moderate. In the majority of patients these reactions started early during treatment, lasted from minutes to hours after each intake of Grazax® and tended to subside spontaneously within 1 to 14 days. If significant local adverse reactions occur, treatment with antihistamines should be considered. Withdrawal due to local reactions may occur in up to 5% of participants due to local side effects of SLIT compared to 3% in placebo-treated participants.

Rare cases of severe systemic allergic reactions have been reported with Grazax® use. Therefore, medical supervision at the start of treatment is an important precaution. All participants will be observed by a study physician for one hour following the first dose of Grazax® and provided with an emergency telephone contact number for study personnel with 24-hour availability. The onset of systemic symptoms may include flushing, itching in the extremities and other areas of the body, general discomfort and agitation. In cases of severe systemic reactions including angioedema, difficulty swallowing or breathing, throat fullness or hypotension, Grazax® should be discontinued and a physician contacted immediately. Severe systemic reactions may be treated with adrenaline. Treatment with Grazax® should remain withheld until evaluation by a study physician.

If participants with concomitant asthma experience symptoms and signs indicating asthma deterioration, treatment should be discontinued and a study physician consulted immediately.

Adverse reactions are divided into groups according to the Medical Dictionary for Regulatory Activities (MedDRA) convention frequencies: Very common ($\geq 1/10$), common ($\geq 1/100$ to $< 1/10$), uncommon ($\geq 1/1,000$ to $< 1/100$), rare ($\geq 1/10,000$ to $< 1/1,000$), very rare ($< 1/10,000$). AEs are reported in Section 4.8 of the SmPC for Grazax® dated December 3, 2018.⁶⁰

5.1.2 DUPIXUMAB: DUPIXENT® AND DUPIXENT® PLACEBO

Dupilumab is generally safe and well tolerated. Warnings and precautions specified in the prescribing information include hypersensitivity reactions, conjunctivitis and

keratitis.³⁰ AE data for dupilumab are provided in Section 4.8 of the SmPC.⁶⁰ Additional safety data from the package insert are provided in Section 1.2.2.

